### ***Analysis of adverse events during the 56-week on study observation period***

The following selected AE will also be summarized for the 56-week on-study observation period as defined in [Section 2.1.4](#):

- Overview of AEs
- AEs (by primary SOC, HLGT, HLT, and PT, showing number (%) of patients with at least 1 adverse event)
- SAE (by primary SOC, HLGT, HLT, and PT, showing number (%) of patients with at least 1 serious adverse event)
- AEs leading to death

### ***Listings***

Supportive AE listings will be provided for all SAEs, AESIs, AERSM, AEs leading to death, and AEs leading to treatment discontinuation. These listings will include at least the following information, sorted by treatment, participant identification, and onset date: treatment, participant identification, country, age, gender, race, randomization strata, primary SOC, PT, reported term, onset date, study day (relative day to the start date of IMP), AE duration, duration of exposure, intensity, corrective treatment, action taken with IMP, relationship to IMP/NIMP, outcome, date of death (if any), seriousness, seriousness criteria, and AE status (“Pre” for a pre-treatment AE; “T” for a TEAE; and “Post” for a post-treatment AE).

Similar to the AE listing, a listing for all adjudicated AEs will be provided with adjudication outcome.

### ***Analysis of COVID-19 related adverse events***

COVID-19 related AEs during the on-treatment period will be presented for the number (%) of participants with at least one event and by primary SOC and PT.

### **2.4.5.2 Analysis of Hypoglycemia**

Treatment-emergent hypoglycemia events will be tabulated separately from the AEs.

Event frequency and incidence of hypoglycemia events will be summarized by treatment for all reported hypoglycemia and per type of hypoglycemic event described in [Section 2.1.4.6](#) (ie, severe, documented symptomatic, asymptomatic, probable symptomatic, relative) for safety population. Incidence of severe or documented symptomatic hypoglycemia events will be summarized by study period ( $\leq 4$  weeks (titration period),  $> 4$  weeks to  $\leq 8$  weeks,  $> 8$  weeks to  $\leq 30$  weeks,  $> 30$  weeks) and according to time of occurrence (nocturnal [ie, 00:00 to 05:59 am], daytime [ie, 06:00 am to 23:59]) for safety population. Documented hypoglycemia (symptomatic or asymptomatic) will be also evaluated for the more stringent plasma glucose threshold of  $< 54$  mg/dL (3.0 mmol/L), as well as for  $\geq 3.0$  and  $< 3.9$  mmol/L ( $\geq 54$  and  $< 70$  mg/dL). Frequency and percentage of participants with at least one hypoglycemia event will be summarized as well.

Event rate of hypoglycemia per participant year will be calculated by treatment using the total number of hypoglycemia events from all participants (denoted as n) divided by the total exposures from all participants expressed in years (ie, participant exposure in days divided by 365.25, denoted as t). Multiple events from an individual participant will all be counted. Event rates of hypoglycemia per participant year {all reported hypoglycemia, severe, documented symptomatic [ $< 54$  mg/dL ( $< 3.0$  mmol/L),  $\geq 54$  and  $< 70$  mg/dL ( $\geq 3.0$  and  $< 3.9$  mmol/L),  $\leq 70$  mg/dL ( $\leq 3.9$  mmol/L) respectively], asymptomatic, probable symptomatic, relative hypoglycemia} will be presented by treatment group during the 56-week on-treatment period.

The summary of frequency and event rate in participant years for severe or documented symptomatic hypoglycemia will be provided as appropriate by gender (Male, Female), age group ( $< 50$ ,  $\geq 50$  to  $< 65$ ,  $\geq 65$  to  $< 75$ ,  $\geq 75$  years), and race (Asian, Black or African American, White, Other).

A KM curve will also be provided by treatment group for the time to first severe or documented symptomatic hypoglycemia during the on-treatment period.

A listing of participants for all severe or documented symptomatic hypoglycemia events reported on the specific eCRF "Hypoglycemic Event Information" page will be provided and sorted by the following order: severe, documented symptomatic.

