### 1.4 STUDY PLAN

This is a multicenter, 56-week, randomized, open-label for the drug (efpeglenatide and dulaglutide) and double-blind for the doses of efpeglenatide, active-controlled, 3-arm, parallel group Phase 3 study consisting of 3 study periods:

- An up to 3-week Screening Period (with a minimum of 11 days)
- A 56-week open-label, active-controlled Treatment Period, for efficacy and safety assessments
- A 6-week post-treatment Follow-up Period to collect safety information after last dose of Investigational Medicinal Product (IMP) after treatment is completed or permanent treatment discontinued

The maximum study duration per participant will be 65 weeks with treatment lasting for 56 weeks. The graphical study design is shown in [Figure 1](#).

Figure 1 - Study Design Overview

Abbreviations: EOS, end of study; EOT, end of treatment; R, Randomization.

Note: The telephone symbol is used to designate visits conducted by telephone interview.

The end of the study is defined as the date of the last visit of the last participant in the study.

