##### *Observation period*

The period related to treatment will be divided into 3 main segments:

- The **pre-treatment** period is defined as the time from informed consent up to the time of first injection of open-label IMP
- The **on-treatment** period is defined as the time from the first injection of the open-label IMP up to 30 days (7 days for hypoglycemia) after the last injection of the IMP
- The **post-treatment** period is defined as the period from the end of the on-treatment period.

The **on-study observation period** is defined as the time from first injection of open-label IMP up to either the last protocol-planned visit or the date of last available information if participants discontinue the study prematurely, whichever is later.

The **post-study observation period** is defined as the time after the end of the on-study observation period until the date of resolution/stabilization of SAE, AESI, and AERSM, up to database lock.

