#### **2.3.1.2 Modified Intent-to-treat population**

Due to the study terminated early by sponsor on September 9, 2020 (hereinafter referred to as “early termination”), the efficacy analyses will be performed in mITT population instead of ITT population originally planned. The mITT population is defined as,

- Participants who have completed the study treatment, or
- Participants who discontinued the study treatment AND completed/discontinued the study before the early termination, or
- Participants who discontinued treatment before early termination and discontinued the study due to early termination within 30 days of the target Week 56 visit (Day 392), or
- Participants who discontinued treatment due to early termination within 30 days of the target Week 56 visit (Day 392).

Participants will not be included in mITT if they discontinued study due to termination and discontinued study treatment (before or due to early termination) and had visits performed more than 30 days before the target Week 56 visit (Day 392).

By-visit summary will be provided for ITT population in addition for mITT population.

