#### **2.4.5.1 Analyses of adverse events**

##### ***Generalities***

The primary focus of AE reporting will be on TEAEs. Pretreatment and posttreatment AEs will be described separately.

If an AE date/time of onset (occurrence, worsening, or becoming serious) is incomplete, an imputation algorithm will be used to classify the AE as pretreatment, treatment-emergent, or posttreatment. The algorithm for imputing date/time of onset will be conservative and will classify an AE as treatment emergent unless there is definitive information to determine it is pretreatment or posttreatment. Details on classification of AEs with missing or partial onset dates are provided in [Section 2.5.3](#).

Incidence tables will present AEs by SOC, HLG, HLT, and PT, sorted in SOC internationally agreed order and HLG, HLT and PT sorted alphabetically for each treatment group, and the number (n) and percentage (%) of participants experiencing an AE. Multiple occurrences of the same event in the same participant will be counted only once in the tables within a treatment phase. The denominator for computation of percentages is the safety population within each treatment group.

Sorting within tables ensures the same presentation for the set of all AEs within the observation period (pretreatment, treatment-emergent, and posttreatment). For that purpose, the table of all TEAEs presented by primary SOC and PT sorted by the internationally agreed SOC order and decreasing frequency of PTs within SOCs will define the presentation order for all other tables unless otherwise specified. In case of equal frequencies of PTs within a SOC, the alphabetic order will be applied. Sorting will be based on the incidence in the efpeglenatide 6 mg group.

The internationally agreed order of SOCs shown below was described in the Introductory Guide MedDRA Version 19.1, September 2016 International Conference on Harmonisation for SOC:

1. Infections and infestations
2. Neoplasms benign and malignant (including cysts and polyps)
3. Blood and lymphatic system disorders
4. Immune system disorders
5. Endocrine disorders
6. Metabolism and nutrition disorders
7. Psychiatric disorders
8. Nervous system disorders
9. Eye disorders
10. Ear and labyrinth disorders
11. Cardiac disorders
12. Vascular disorders
13. Respiratory, thoracic, and mediastinal disorders
14. Gastrointestinal disorders
15. Hepato-biliary disorders
16. Skin and subcutaneous tissue disorders

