- The frequency of TEAEs over time will be provided for nausea, vomiting and diarrhea, using weekly time intervals up to 56 weeks, ie, [0-1] week, [1-2] weeks, [2-3] weeks, [3-4] weeks, etc. In each time interval, the numerator in the calculation of percentages will be the number of participants with at least 1 TEAE occurring in this time interval. Two types of analyses will be included: (1) only the first event will be counted for each participant and all recurrent events will not be included, and the denominator for the calculation of percentages will be the number of participants at risk at the beginning of the time interval who did not experience a first event in the preceding intervals; and (2) the recurrent events in subsequent intervals will be counted once for each participant in the numerator of the corresponding interval, and the denominator for the calculation of percentages will be the number of participants at risk at the beginning of the time interval. A histogram of the frequency over time (by weekly intervals) will also be presented as appropriate.
- All TEAEs by BMI subgroup (< 30, ≥ 30 kg/m^2)
- All TEAEs by Anti-Efpeglenatide Antibody Status (Positive, Negative)

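### Hypoglycemia percentages by study period (SAP 2.4.5.2) have no exposure basis, so they are not a reliable guide to how risk changes over time

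*SAP*

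**What the plan says.** SAP 2.4.5.2 states: "Incidence of severe or documented symptomatic hypoglycemia events will be summarized by study period". The cut-points are Weeks 4, 8 and 30, the first period is labelled as titration, and the last has no stated end. The same sentence also covers nocturnal and daytime events and closes with "daytime [ie, 06:00 am to 23:59]) for safety population". No denominator for each period and no exposure for each period is given.

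Other parts of the SAP bear on how this is read:

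- Section 2.3.2 puts in the safety population any randomized participant who received at least part of a dose, with no condition on reaching a given week.
- Section 2.4.5.1 (Generalities) sets a default for adverse event tables: "The denominator for computation of percentages is the safety population within each treatment group".
- Section 2.4.5.1 departs from that default for weekly nausea, vomiting and diarrhea, where "the denominator for the calculation of percentages will be the number of participants at risk at the beginning of the time interval".
- Section 2.4.5.2 does plan hypoglycemia rates per participant-year over the whole on-treatment period by arm, and by gender, age and race for this same event. It does not plan them by study period. It also plans a Kaplan-Meier curve by arm for time to the first such event.
- Section 2.3.1.2 records the termination: "Due to the study terminated early by sponsor on September 9, 2020". The modified intent-to-treat population created in response concerns efficacy. The table of SAP changes lists nothing for 2.4.5.2.

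**The concern.** A table of hypoglycemia by period invites a reader to ask whether events cluster during titration or appear later. Crude percentages answer that only if the periods are similar in length and nearly everyone is observed through each one. Here the last period is about six and a half times as long as the first, and follow-up is shortened both by ordinary discontinuation and by the sponsor's termination of the study.

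The SAP uses an at-risk denominator for gastrointestinal events by interval and exposure-adjusted rates for hypoglycemia overall. It carries neither into the one hypoglycemia table where exposure differs most between columns. Two of the three secondary safety endpoints in protocol Section 3 concern hypoglycemia, so the table will be read.

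**Working it through.** **Plan figure.** Neither document gives a hypoglycemia rate, an expected percentage by period, or a count of participants on treatment at Week 30. There is therefore no figure of the plan's own to reproduce on this point, and what follows illustrates the mechanism on assumed inputs.

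**Inputs from the documents.** The cut-points are 4, 8 and 30 weeks (SAP 2.4.5.2). Planned treatment is given in SAP 1.4: "A 56-week open-label, active-controlled Treatment Period, for efficacy and safety assessments". The period lengths are therefore 4, 8 − 4 = 4, 30 − 8 = 22 and 56 − 30 = 26 weeks. The 26 is derived. It can run slightly longer, because SAP 2.1.4 extends the on-treatment period "up to 30 days (7 days for hypoglycemia) after the last injection of the IMP".

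**Assumed inputs.** A constant rate of 0.05 to 0.5 first events per participant-year; 50% to 100% of the safety population entering the last period; entrants completing all or half of it.

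**Step 1: length alone, full follow-up.** Incidence = 1 − exp(−rate × weeks × 7/365.25). At 0.10 per participant-year:

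- 4 weeks: 1 − exp(−0.00767) = 0.76% (first and second periods)
- 22 weeks: 1 − exp(−0.04216) = 4.13%
- 26 weeks: 1 − exp(−0.04983) = 4.86%

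The last period shows 6.37 times the percentage of the first, although risk per unit time is constant. Across rates of 0.05 to 0.5, the ratio to the first period is 5.05 to 5.45 for the third and 5.86 to 6.43 for the last. This effect raises the later percentages.

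**Step 2: early stopping, if the denominator is the whole safety population.** Last period, rate 0.10. The whole-population percentage is the share entering multiplied by the at-risk percentage. If entrants complete half the period (13 weeks), the at-risk percentage is 1 − exp(−0.02491) = 2.46%.

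| Share entering | Complete all 26 weeks: whole population | At risk | Complete half: whole population | At risk |
|---|---|---|---|---|
| 100% | 4.86% | 4.86% | 2.46% | 2.46% |
| 90% | 4.37% | 4.86% | 2.21% | 2.46% |
| 70% | 3.40% | 4.86% | 1.72% | 2.46% |
| 50% | 2.43% | 4.86% | 1.23% | 2.46% |

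This effect lowers the later percentages and so opposes Step 1. The comparison of the last two periods shows what that can do. With full follow-up the last exceeds the third (4.86% against 4.13%). If 70% enter and complete the last period, and all leavers go at Week 30, it falls below it (3.40% against 4.13%). The switch comes at 4.13/4.86 = about 85% entering. The true rate is the same throughout.

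**Step 3: what each remedy corrects.** The at-risk denominator restores 4.86% when entrants complete the period. When they complete half, it still gives 2.46%, because it does not account for those who leave partway. It also leaves the unequal lengths of Step 1 untouched. Events divided by participant-years within the period give 0.10 in every period and every row above.

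**The case against.** The case for leaving the table alone has real substance.

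1. **The Kaplan-Meier curve covers the same event.** It accounts for early stopping and shows by arm when first events occur. This stands, and it means the trial will not lack information on first-event timing. The curve does not correct the period table, though, and it ignores repeat events.

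2. **The denominator is not stated.** A reader might infer that the SAP fixes the whole safety population as the denominator here. It does not. The default sentence sits in the adverse event section, and 2.4.5.2 tabulates hypoglycemia separately. The weekly gastrointestinal tables also belong to a list produced for the safety population yet use an at-risk denominator, so naming a population does not settle the matter. The whole-population reading is natural but inferred. The unequal-length effect does not depend on it.

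3. **Numbers on treatment can be approximated.** SAP 2.4.3.1 tabulates exposure cumulatively with limits that include 4, 8 and 30 weeks. This stands in part: durations are rounded to whole weeks and ignore interruptions, and the table gives no events or participant-years by period.

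4. **The cut-points have a reason and the table tests nothing.** Week 4 ends titration, and Weeks 8 and 30 are points at which the protocol's rescue thresholds change. The period labels show the unequal widths. SAP 2.4.5 describes the safety analysis as essentially descriptive. All of this stands, and it keeps the point minor.

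**Conclusion.** The crude percentages by period are not a reliable guide to how hypoglycemia risk changes over time, because they mix risk with period length and with truncated follow-up. On an assumed constant rate of 0.05 to 0.5 per participant-year with full follow-up, length alone makes the last period look about six times the first. Early stopping works in the opposite direction if the whole safety population is the denominator. Its size is unknown, because the documents give no discontinuation counts.

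Two stronger readings are tempting and go too far. A reader might infer that later-period risk is understated. The documents do not support that as a net statement: the two distortions oppose each other, and neither the direction nor the size of their sum can be fixed. A reader might also infer that the periods cannot be compared at all. The planned Kaplan-Meier curve allows first-event risk to be read over each interval, and arms can be compared within a period if their exposure is similar.

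No test, error rate or efficacy conclusion is affected. This is a worthwhile, low-cost improvement to one descriptive table.

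**What to change.** In SAP 2.4.5.2:

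- Add, for each study period and arm, the participant-years of exposure and the number of severe or documented symptomatic events per participant-year, using the formula already in that section with exposure split at Weeks 4, 8 and 30. This is the more important part, because it handles unequal length, non-entry and partial completion, and it counts repeat events.
- State the denominator for the period percentages as participants still in the on-treatment period (including the 7 days after the last injection) when the study period starts, whether or not they had an earlier event. This matches the second of the two interval analyses for nausea, vomiting and diarrhea in 2.4.5.1. Show that number in each column.

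The cost is one or two sentences and a few extra rows in one table. The first and last dose dates and the event dates are already collected, so no new data are needed.

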### 3 OBJECTIVES AND ENDPOINTS

**Table 1 - Objectives and endpoints**

Objectives	Endpoints
Primary	
To demonstrate the noninferiority of once-weekly injection of efpeglenatide 4 or 6 mg in comparison to once-weekly injection of dulaglutide 1.5 mg on HbA1c change from baseline to Week 56 in participants with T2DM inadequately controlled with metformin	
 
Change from baseline to Week 56 in HbA1c
 

Secondary	
To demonstrate the superiority of once-weekly injection of efpeglenatide 4 and 6 mg with once-weekly injection of dulaglutide 1.5 mg on glycemic control	
 
Change from baseline to Week 56 in fasting plasma glucose (FPG)
 
Number of participants with HbA1c <7.0% at Week 56
 

To demonstrate the superiority of once-weekly injection of efpeglenatide 4 and 6 mg with once-weekly injection of dulaglutide 1.5 mg on body weight	
 
Change from baseline to Week 56 in body weight
 

To evaluate the safety of once-weekly injection of efpeglenatide 4 and 6 mg and once-weekly injection of dulaglutide 1.5 mg	
 
Number of participants with at least one hypoglycemic event during treatment period
 
Number of hypoglycemic events per participant-year during treatment period
 
Number of participants with AEs (see Section 8.3)
 

Tertiary/exploratory	
To evaluate the immunogenicity of once-weekly injection of efpeglenatide 4 and 6 mg	
 
Number of participants by ADA status (positive/negative) at scheduled visits
 
Number of participants with treatment-induced ADAs (among the participants ADA negative or missing at baseline) during the study period
 
Number of participants with treatment-boosted ADAs (among the participants with ADA positive at baseline) during the study period
 
ADA titer at scheduled visits
 
Number of participants by ADA cross-reactivity to endogenous GLP-1 at scheduled visits
 
Number of participants by ADA cross-reactivity to endogenous glucagon at scheduled visits
 
Number of participants with ADAs directed against PEG linker of efpeglenatide at scheduled visits
 

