- Initiate an evaluation and treatment of intercurrent disease (to be reported in AE/concomitant medication parts of the electronic Case Report Form [eCRF] and the medical record)

- Stress the absolute need for the participants to be compliant with treatment
- Organize a specific interview with the participants and a Registered Dietician or other qualified nutrition professional to reinforce the absolute need to be compliant with diet and lifestyle recommendations, and schedule an FPG and/or HbA1c assessment at the next visit

If none of the above-mentioned reasons can be found, or if an appropriate action fails to decrease FPG and/or HbA1c to below the threshold values, rescue medication(s) may be introduced.

If a participant needs to start rescue therapy, an unscheduled in-person visit will be scheduled to perform pre-rescue assessments (which are the same as those specified for EOT; Week 56 [Visit 14]), prior to starting the rescue medication(s).

Prescription of open-label rescue medication(s) to treat hyperglycemia will be at the discretion of the Investigator and in accordance with local standards of care and prescribing practice. With the exception of other GLP-1 RAs and DPP-4 inhibitors, any approved medication(s) can be prescribed to treat the hyperglycemia.

If a participant requires glycemic rescue, the IMP received during the randomized, open-label Treatment Period should be continued (unless the Investigator considers a change necessary for safety reasons) and the efpeglenatide dose must remain blinded until the end of the study.

All concomitant antidiabetic medications (background metformin and/or rescue therapy) will be documented in the eCRF. The cost of NIMPs not covered by health insurance will be reimbursed by the study Sponsor where permitted by local regulations.

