### Background medication

Metformin tablets, administered as per Principal Investigator prescription and in accordance with local labeling, and rescue medication(s) that will be used to treat hyperglycemia if a participant's glycemic values reach the applicable rescue threshold.

The doses of metformin at randomization should be maintained throughout the study unless down-titration is required for safety reasons.

**Rescue medication(s)** is considered Non-IMP (NIMP) treatment. Except for GLP-1 RA and DDP-4i, any approved medication(s) including oral antidiabetic drugs or insulin can be prescribed at the Investigator's discretion to treat the hyperglycemia.

The background medication and rescue medications will be included in the concomitant medication summaries. A special list of rescue therapy medications will be generated.

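### Hypoglycemia is counted through rescue therapy, and no planned table separates events before rescue from events after it

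*SAP*

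**What the plan says.** Protocol Table 1 lists two hypoglycemia endpoints under the secondary safety objective: "Number of participants with at least one hypoglycemic event during treatment period" and "Number of hypoglycemic events per participant-year during treatment period".

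The SAP sets the on-treatment period in section 2.1.4 as "the first injection of the open-label IMP up to 30 days (7 days for hypoglycemia) after the last injection of the IMP". The rate in SAP 2.4.5.2 is defined as follows: "Event rate of hypoglycemia per participant year will be calculated by treatment using the total number of hypoglycemia events from all participants", divided by total exposure in years. It adds: "Multiple events from an individual participant will all be counted". Exposure (SAP 2.4.3.1) is last dose date minus first dose date plus 7 days.

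On rescue, Protocol 6.1.2.2 says: "If a participant requires glycemic rescue, the IMP received during the randomized, open-label Treatment Period should be continued", unless the investigator sees a safety reason to change it. GLP-1 receptor agonists and DPP-4 inhibitors are barred as rescue. Otherwise, in SAP 2.1.2, "any approved medication(s) including oral antidiabetic drugs or insulin can be prescribed".

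The breakdowns in SAP 2.4.5.2 are by event type, glucose threshold, study period, time of day, gender, age and race. Rescue status is not among them. The Kaplan-Meier curve for the first severe or documented symptomatic event also uses the whole on-treatment period. The only planned analysis that leaves out rescued participants is the HbA1c completers analysis in SAP 2.4.4.1.

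**The concern.** Rescue happens after randomization and is triggered by poor glycemic control, which is the efficacy outcome of the trial. It can therefore differ between arms. The decision also rests partly on the judgment of investigators who know which drug the participant receives (Protocol 6.1.2.2 and 6.3.1). Participants enter on metformin alone, and Protocol 2.2 describes the GLP-1 class as carrying a low risk of hypoglycemia. Against a low background, added insulin could supply a noticeable share of the events.

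An arm with weaker glycemic control could then show more hypoglycemia through its rescue drugs alone. The planned tables would not let a reader tell that from a property of the study drug. What is at stake is the interpretation of two secondary safety endpoints. No hypothesis test depends on them.

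**Working it through.** **Plan's own figures.** The documents give no expected hypoglycemia rate, rescue share or effect of rescue drugs, so there is no figure on this point to reproduce. The one design figure is 91% power for HbA1c noninferiority (300 per arm, SD 1.1, margin 0.3). It reproduces: SE = 1.1 × √(2/300) = 0.0898, 0.3/0.0898 − 1.96 = 1.38, power 91.6%. It plays no part below.

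**Tracing one rescued participant through the rules.**

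1. Rescue starts and study drug continues (Protocol 6.1.2.2).
2. The hypoglycemia window stays open until 7 days after the last injection (SAP 2.1.4).
3. Every later event enters the numerator, and later time on study drug enters the denominator (SAP 2.4.5.2 and 2.4.3.1).
4. For the incidence endpoint, a first event after rescue makes the participant a case.
5. No table, curve or sensitivity analysis removes or labels these events.

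**Size for the event rate, on assumed inputs.** Take the same pre-rescue rate in both arms. Let r be the share rescued, f the share of a rescued participant's exposure that falls after rescue, and m the post-rescue rate as a multiple of the pre-rescue rate. The arm's rate relative to its pre-rescue rate is

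(1 − r·f) + m·r·f = 1 + r·f·(m − 1).

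The apparent rate ratio is this quantity for the arm with more rescue divided by the same quantity for the other arm. Example for 5% against 10%, f = 0.5, m = 10: (1 + 0.10 × 0.5 × 9)/(1 + 0.05 × 0.5 × 9) = 1.45/1.225 = 1.184.

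| Rescued | f = 0.3, m = 2 | f = 0.3, m = 10 | f = 0.5, m = 5 | f = 0.5, m = 10 |
|---|---|---|---|---|
| 5% vs 5% | 1.000 | 1.000 | 1.000 | 1.000 |
| 3% vs 6% | 1.009 | 1.075 | 1.057 | 1.119 |
| 5% vs 10% | 1.015 | 1.119 | 1.091 | 1.184 |
| 5% vs 15% | 1.030 | 1.238 | 1.182 | 1.367 |

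With m = 1 every ratio is 1.00. Equal rescue removes the distortion of the ratio, but each arm's own rate still includes rescue-drug events: at 5% rescued it is 1.015 to 1.225 times the pre-rescue rate.

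**Against sampling noise.** Assume a pre-rescue rate of 0.2 per year, 300 person-years per arm, f = 0.35 and m = 10, with 5% against 10% rescued. The rates are 0.2 × 1.1575 = 0.2315 and 0.2 × 1.315 = 0.263, or about 69 and 79 events. The ratio is 1.14. With SE of the log ratio √(1/69 + 1/79) ≈ 0.165, the Poisson 95% interval is about 0.82 to 1.57, and wider if events cluster within participants. With m = 2 the rates are 0.2035 and 0.207, ratio 1.02.

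**The case against.** The strongest reply is that counting every on-treatment event is a choice, and a sound one. It describes what happens to participants under the randomized strategy, rescue included. SAP 2.4.4 takes the same approach for efficacy by keeping post-rescue values, and SAP 2.1.4.6 evaluates hypoglycemia whatever its time of onset. The safety objective in Protocol Table 1 is to evaluate, not to demonstrate a difference. SAP 2.4.5 makes the safety analyses essentially descriptive, and hypoglycemia is outside the testing hierarchy in SAP 2.4.4.3.

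The reader also has some indirect evidence. Rescue use and time to rescue are shown by arm (SAP 2.4.4.4.6 and 2.4.4.4.7), rescue drugs are listed, and severe or documented symptomatic events are both listed and summarized by study period. The intervals up to Week 8 should hold little rescue, since the threshold then is high and based on fasting glucose only (Protocol Table 3).

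Most of this stands. The all-events tables are legitimate and should stay, and no error rate is affected. Two things remain. The SAP does not say that the hypoglycemia tables deliberately include rescue-drug events. And the indirect displays can reveal an imbalance in rescue but give no pre-rescue rate, least of all after Week 30, where the thresholds are tightest. SAP 2.4.5 also allows relative risks between arms with confidence intervals, so an arm comparison may well be reported.

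A reader might infer that the pre-rescue version should replace the planned one as the main comparison. The documents do not support that. It answers a different question, and cutting at rescue is itself informative, because it removes time from participants selected for poor control. It would also move severe events during combined use out of the main safety display.

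**Conclusion.** The point holds as a gap in presentation. Both secondary hypoglycemia endpoints mix events before and after rescue, and nothing planned separates them. A distorted arm comparison needs two conditions together: unequal rescue, and rescue drugs that change the hypoglycemia rate. The documents establish neither.

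On the assumed ranges (30% to 50% of a rescued participant's exposure after rescue, a 2- to 10-fold post-rescue rate), the apparent ratio between identical drugs is 1.015 to 1.18 for 5% against 10% rescued, and up to 1.37 for 5% against 15%. It is 1.00 if either condition fails. These figures concern the event rate; the incidence endpoint is open to the same mixing but was not quantified.

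A reader might go further and conclude that the planned hypoglycemia results are invalid, or biased against a particular arm. The text does not show that: the direction and size depend on data that the plan does not forecast, and at moderate imbalance the effect could lie within sampling noise. The addition is worth making because it is cheap and lets the trial separate the two sources of hypoglycemia.

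**What to change.** In SAP 2.4.5.2:

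- Keep the planned all-events tables and add one sentence saying that they include events after the start of rescue therapy.
- Add beside them both secondary hypoglycemia endpoints, and severe or documented symptomatic events, with events and exposure cut at the first dose of rescue. State which side of the cut the day of that dose falls on.
- Take the cut from the rescue start dates already needed for time to rescue (SAP 2.4.4.4.7), with the partial-date rule in SAP 2.5.3.
- State that the two versions are read together, and why the cut is informative.

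Do not apply a hypoglycemia-only cut to the summary in SAP 2.4.4.4.9 of HbA1c below 7.0% without severe or documented symptomatic hypoglycemia. SAP 2.4.4.2.1 accepts HbA1c values obtained after rescue when classing responders. Cutting hypoglycemia alone would therefore credit a participant who reached the target on rescue and had hypoglycemia from it. If a pre-rescue composite is shown, rescued participants must be handled in the HbA1c component too, for example by counting them as not meeting it.

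The cost is one cut-off variable and a few repeated tables, with slightly less exposure in the added version. Clinical management does not change.
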